1. Patients will come to the Emergency Department or the POC after a supracondylar fracture or periprosthetic distal femur fracture. 2. If they fit all the inclusion and none of the exclusion criteria they will be told about the study either before their surgery if they are lucid, not in pain and can understand the study, or after their surgery when they are lucid, not in pain and can understand the study. If they are not lucid, are in pain, or cannot understand the study during this time they will not be offered participation in the study. 3. They will be told about the study with the understanding that assignment to either partial weight bearing or full weight bearing is standard of care and that physical therapy will conduct the therapy based on their group assignment 4. All questions will be answered and the subject will be given the opportunity to consent 5. They will have a metabolic bone work up done if they are 65 years of age or older which is standard of care. 6. Radiographs will be taken at 6 weeks, 3, 6 and 12 months to determine radiographic healing and/or complications with hardware which is standard of care. 7. Two independent surgeons will review radiographs to determine bridging of 3 or 4 cortices 8. We will measure time to ambulation at 2 weeks, 6 weeks and 3 months. Other variables measured include: Age, gender, date of surgery, Surgeon, Rt/Left, plate (LISS or Locking), smoking status, co-morbidities, perambulatory status, PT participation, time to discharge, discharge disposition, return to baseline ambulation, time to union, pain, Knee society score, knee flexion, radiographic evidence of healing, non-union, malunion, infection, DVT, PE, implant failure/reoperation, Vit D level, death. 9. Patients will complete a health progress report at 2 weeks, 3, 6, and 12 months post-surgery which is standard of care.

Please describe the investigational procedures that will be performed throughout the duration of the study.

Reviewing who heals faster with better outcomes based on assignment to full or partial weightbearing, both of which are standard of care, but for the study, the subject is assigned to one or the other.

Please describe the standard of care procedures that will be performed throughout the duration of the study.

Surgery and anything associated with it.

Will you be assigning or randomizing participants to groups or conditions (e.g., control, placebo)?

Yes

Describe the group assignment.

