We will be looking at two groups: those with periprosthetic distal femur fracture and those with a distal femur fracture proximal to the native knee. Both will have had their distal femur fracture repaired per standard of care. Patients in both groups will then be randomized into two groups: those allowed to bear weight immediately post operatively and those with protected weight bearing post operatively.

Does the research involve surveys/interviews/questionnaires? If so, attach a copy of the interview/survey questions on the Notes & Attachments page.

No

Describe what is known about this topic and why this study is needed. Please include at least two reference citations to support your rationale.

This study is designed to examine if immediate weight bearing on a distal femur fracture fixed with a primary locking plate, either a distal condylar locking plate or a LISS (less invasive stabilization system), is safe and promotes more rapid fracture healing. Historically and currently patients are kept partial weight bearing after fixation of these fractures for 6-12 weeks until callous formation is observed on radiographs. Our hypothesis is that patients that are allowed to bear weight immediately will heal at least as quickly as those that have their weight bearing status protected with the added benefits from early mobilization. Fracture healing will be monitored closely by follow up appointments and complications will be documented. See Lit Review under Notes and Attachments for Scientific Rationale and references.

What method are you going to use to analyze the data?

Descriptive statistics will be performed on the following variables in both groups: Age, gender, date of surgery, Surgeon, Rt/Left, plate (LISS or Locking), smoking status, co-morbidities, perambulatory status, PT participation, time to discharge, discharge disposition, return to baseline ambulation, time to union, pain, Knee society

score, knee flexion, radiographic evidence of healing, non-union, malunion, infection, DVT, PE, implant failure/reoperation, Vit D level, death.

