### Subjects

Indicate the maximum number of subjects to be enrolled or medical records to be reviewed at all sites by the WVU or VAMC research team.

150

Provide a rationale for choosing your sample size.

75 in each group provides 80% power to detect a difference between the groups.

State the requirement(s) to become a participant in the study (e.g., age range, sex, language spoken, class enrollment/ranking).

All patients aged > 18 yo with a distal supracondylar femur fracture will be included, both male and female; Supracondylar distal femur fractures treated with a locked plate, either a distal condylar locking plate or a LISS (less invasive stabilization system), including peri-prosthetic fractures. CPT code 27511

Explain why selection of participants will be equitable addressing gender, ethnicity, and/or race of subjects.

Patients with an intracondylar split, polytrauma patients with associated trauma that will inhibit their ability to weight bear, metastatic disease, incomplete follow up, those with questionable ability to bear weight (ie advanced dementia), open fractures with bone loss, will not be included. Those who are in pain, not lucid, or unable to understand the study at time of consent will not be included.

In outline format and chronological order, describe what will be done to identify and recruit participants (e.g., A, B, C or 1, 2, 3).

1. Patients will come to the Emergency Department or the POC after a supracondylar fracture or periprosthetic distal femur fracture. 2. If they fit all the inclusion and none of the exclusion criteria they will be told about the study either before their surgery if they are lucid, not in pain and can understand the study, or after their surgery when they are lucid, not in pain and can understand the study. If they are not lucid, are in pain, or cannot understand the study during this time they will not be offered participation in the study.

Will any of the subjects be less than 18 years old?

No

Will your study target populations such as pregnant women, fetuses, neonates, or any groups likely to be vulnerable to coercion or undue influence such as children, prisoners, individuals with impaired decision-making capability or economically or educationally disadvantaged persons?

No

Does this research involve participants who could be coerced or unduly influenced, such as current students/employees of research team members?

No

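### Patients are split by fracture type before randomisation, but fracture type is in neither variable list nor the analysis, and the word group serves for both fracture type and arm

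*Combined protocol and SAP*

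**What the plan says.** The group-assignment answer in the Design section begins with fracture type: "We will be looking at two groups: those with periprosthetic distal femur fracture and those with a distal femur fracture proximal to the native knee". Two sentences later it says "Patients in both groups will then be randomized into two groups", and these second two groups are the weight-bearing arms. It mentions no strata, separate lists, blocks or allocation ratio.

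Item 8 of the procedures, in the same section, gives the data to be collected: "Other variables measured include: Age, gender, date of surgery, Surgeon, Rt/Left, plate (LISS or Locking), smoking status", followed by further clinical and outcome variables. Surgeon, side and plate type are there. Fracture type (periprosthetic or native knee) is not. The analysis answer repeats essentially the same list, again without fracture type, and its whole method is "Descriptive statistics will be performed on the following variables in both groups". It names no test, model, interval, adjustment or subgroup.

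The eligibility answer in the Subjects section admits both types ("including peri-prosthetic fractures"). The sample-size rationale is one sentence: "75 in each group provides 80% power to detect a difference between the groups". The maximum enrolment is 150.

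**The concern.** Fracture type is the first feature the plan gives its design, and it then disappears. Two things follow.

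First, a factor that appears to govern randomisation should normally enter the analysis. If it is balanced by design and then ignored, the standard error of the arm difference is overstated. If it is not balanced by design, it is a baseline factor on which the arms can differ by chance, and the reader needs to see it. Neither is provided for when the factor is not a listed variable. Interval width matters here because the hypothesis is that early weight bearing heals at least as quickly.

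Second, the same word names the fracture types and the arms within a single answer, and is then used without definition in the analysis sentence and the sample-size sentence. Someone producing the tables has to infer that the columns are the randomised arms.

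**Working it through.** **1. The plan's own figure.** The stated 80% power cannot be reproduced, because the Subjects section gives no endpoint, effect size, variability, event rate, significance level or sidedness. As a reference point I assume a continuous outcome, 1:1 allocation, a two-sided 5% test, and exactly 80% power at 75 per arm when fracture type is ignored and explains nothing:

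standardised difference = (1.960 + 0.842) × √(2/75) = 2.802 × 0.1633 = 0.458.

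The true effect is then 2.802 standard errors. Other effects give other powers at 75 per arm (45% at 0.3, 69% at 0.4, 86% at 0.5), so 80% is neither confirmed nor refuted.

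**2. Allocation balanced by fracture type.** Let R² be the share of outcome variance explained by fracture type. The documents give no value; I assume 2% to 10%. The true standard error of the arm difference is √(1 − R²) times the one an unadjusted analysis reports. Hence:

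- type I error, unadjusted = 2 × [1 − Φ(1.960/√(1 − R²))]
- power, unadjusted = Φ(0.842/√(1 − R²))
- power, adjusted = Φ(2.802/√(1 − R²) − 1.960)

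| R² (assumed) | Type I error, unadjusted | Power, unadjusted | Power, adjusted |
|---|---|---|---|
| 0 | 5.0% | 80.0% | 80.0% |
| 0.02 | 4.8% | 80.2% | 80.8% |
| 0.05 | 4.4% | 80.6% | 82.0% |
| 0.10 | 3.9% | 81.3% | 84.0% |

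For example, at R² = 0.10, √0.90 = 0.949. Then 1.960/0.949 = 2.066 gives 3.9%, 0.842/0.949 = 0.887 gives 81.3%, and 2.802/0.949 − 1.960 = 0.993 gives 84.0%. Ignoring fracture type costs about 0.5 points of power at R² = 0.02 and 2.7 points at 0.10. The reported standard error is too large by 1/√(1 − R²) − 1, which is 1% to 5%.

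**3. Simple allocation.** The unadjusted test then keeps its 5% level on average, so the type I error column does not apply. The issue is chance imbalance. With a periprosthetic share p (assumed 30% to 50%), the 95% range for the difference in that share between arms is ±1.96 × √(2p(1 − p)/75):

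- p = 0.30: 1.96 × √(0.42/75) = 14.7 percentage points
- p = 0.50: 1.96 × √(0.50/75) = 16.0 percentage points

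The listed variables contain nothing from which such a difference could be reported or adjusted for.

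**4. The wording.** In the group-assignment answer the word first means fracture type and then means arm. The later uses, in the analysis sentence and in the sample-size sentence, carry no qualifier. The procedures, however, state the contrast of interest as assignment to full or partial weight bearing.

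**The case against.** The strongest reply is that little is demonstrably wrong. The plan never says randomisation is stratified, and simple randomisation of a mixed population also fits the text. With only descriptive statistics planned, no test or interval exists whose width could be wrong, and the absence of any comparative analysis is the larger gap. The R² range has no support in the documents, and the linear-model formulas do not carry over directly to time to union. All of this stands, and it is why the size above is conditional.

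Three stronger readings are tempting but not supported.

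- **That the 75 refers to each fracture type.** Each type would then have 37.5 patients per arm, and power within a type for the 0.458 effect would be about 51%. But the lay summary, the procedures and the Potential Benefits section all make weight bearing the contrast, no recruitment quota by fracture type is described, and the last groups defined before the analysis sentence are the arms. The wording needs repair; it does not show a loss of power.
- **That fracture type will be unrecoverable.** The variable list is open-ended and also omits the assigned arm, which must be recorded. Fracture type is evident at presentation, the data come from medical records, and an identifier file is kept. It could be retrieved while those records last, although the plan does not provide for it.
- **That ignoring the stratum drops power from 81–84% to 80%.** Under balanced allocation the unadjusted analysis already has 80.2% to 81.3%, so the loss is smaller.

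**Conclusion.** The point holds in limited form. Fracture type structures the design, most naturally as a randomisation stratum, yet it is in neither variable list nor the analysis, and one word is used for both fracture type and arm.

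A reader might infer that the planned comparison is biased or that it discards a specified stratification. The documents support neither. Omitting a balanced factor leaves the arm contrast unbiased for a continuous outcome, and neither a stratified scheme nor a comparison is actually specified.

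The cost is modest: a somewhat conservative test and 0.5 to 2.7 points of power if allocation is balanced, or an invisible chance imbalance of up to about 15 to 16 percentage points if it is simple. These figures rest on the assumed R² of 2% to 10%, a continuous outcome, a two-sided 5% test, 75 per arm set at 80% power, and a periprosthetic share of 30% to 50%. At R² = 0 adjustment gains nothing. The change is worth making because it is nearly free and removes a real ambiguity.

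**What to change.** - Add fracture type (periprosthetic or native knee) to the variables in item 8 of the procedures and in the analysis answer.
- State whether randomisation is stratified by fracture type.
- Use arm and fracture type as separate terms throughout. In the sample-size rationale, write 75 per weight-bearing arm, fracture types combined.
- Specify the analysis as a comparison of the two weight-bearing arms, stratified by or adjusted for fracture type. Radiographs are scheduled only at 6 weeks and at 3, 6 and 12 months, so union times are grouped and heavily tied. A discrete-time or interval-censored model with a fracture-type term would suit union; a model term or Mantel-Haenszel stratification would serve for other outcomes.
- Report the arm effect within each fracture type with confidence intervals, labelled descriptive.

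The cost is one data field, one model term and some rewording, with no extra patients, visits or procedures. For patients already enrolled, fracture type can be taken from the medical record.

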**Design**

Please provide a lay summary (written at 6th grade level) that includes a statement about the purpose and the general aims of the research.

This study is designed to examine if immediate weight bearing on a distal femur fracture fixed with a primary locking plate, either a distal condylar locking plate or a LISS (less invasive stabilization system), is safe and promotes more rapid fracture healing. Historically and currently patients are kept partial weight bearing after fixation of these fractures for 6-12 weeks until callous formation is observed on radiographs. Our hypothesis is that patients that are allowed to bear weight immediately will heal at least as quickly as those that have their weight bearing status protected with the added benefits from early mobilization. Fracture healing will be monitored closely by follow up appointments and complications will be documented.

Fully describe all procedures to be performed, from start to finish, numbering your procedures 1,2,3 or A, B, C (e.g., 1. Recruiting, 2. Consent, 3. Collecting data, 4. How findings will be shared, etc.).

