### **Potential Benefits**

Is there any known benefit to the individual subject as a result of participating in the research? Payments to subjects should not be included in this section, but addressed in the Payments/Reimbursements section.

If our hypothesis is correct, those subjects who do full weight bearing will heal faster and suffer less complications.

Describe the potential benefit(s) to society and/or scientific / medical knowledge of the planned work.

Understanding and sharing information gathered from the research study re: benefit or no benefit to full weight bearing after a supracondylar distal femur fracture.

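### The only planned analysis is descriptive, so the randomised comparison of healing has no outcome, estimate or test, and the 80% power belongs to no planned analysis

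*Combined protocol and SAP*

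**What the plan says.** The Design section puts the question of analysis method directly. The whole answer is "Descriptive statistics will be performed on the following variables in both groups" and a list that runs from age and surgeon to time to union, non-union, infection, reoperation and death. The same section has patients randomised to immediate or protected weight bearing. It uses the word group both for the two fracture types and for the two arms; I read the analysis and sample-size sentences as meaning the arms.

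Under Subjects, the rationale for 150 patients is one sentence: "75 in each group provides 80% power to detect a difference between the groups".

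The objective is worded in more than one way. The aim in the Design section is to learn whether immediate weight bearing "is safe and promotes more rapid fracture healing". The hypothesis that follows, given identically in the lay summary and the rationale, is that "patients that are allowed to bear weight immediately will heal at least as quickly as those that have their weight bearing status protected". The Potential Benefits section says: "If our hypothesis is correct, those subjects who do full weight bearing will heal faster and suffer less complications".

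Healing is observed at fixed visits: "Radiographs will be taken at 6 weeks, 3, 6 and 12 months to determine radiographic healing". The reading rule is "Two independent surgeons will review radiographs to determine bridging of 3 or 4 cortices", with no single threshold chosen. The exclusions under Subjects include "metastatic disease, incomplete follow up, those with questionable ability to bear weight".

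**The concern.** A randomised trial with a power claim implies a comparison, and this plan does not contain one. Followed to the letter, it would produce summaries of more than twenty variables by group and no inference on the question it was set up to answer. Power is a property of a test of a stated effect on a stated outcome; none of the three is given.

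The secondary problem is the objective. Showing that healing is no slower needs a margin and a confidence limit; showing that it is faster needs a test of difference. With neither fixed, a test added later that proves non-significant could be presented as support for the hypothesis, although non-significance does not show equal healing.

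The third problem is that completeness of follow-up can be known only after enrolment. If that exclusion were applied after randomisation, it would remove randomised patients, and it could bias the comparison wherever loss is related to healing.

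**Working it through.** **The plan's own figure.** The inputs in the documents are 75 per group and 80% power (Subjects). Outcome, effect, standard deviation or union rate, alpha, number of sides, margin and loss are not stated. The 80% can therefore be neither reproduced nor refuted. What can be done is to hold 75 per arm and 80% fixed, assume a two-sided 5% test, and solve for the effect, with z = 1.960 + 0.842 = 2.802:

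- Continuous outcome: 2.802 × √(2/75) = 0.457 SD. Power is 69% for 0.40 SD and 45% for 0.30 SD.
- Proportion united: 80% against 95%, for example.

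The sentence is true for these effects and false for smaller ones, and nothing says which effect is meant.

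**What the trial could show about healing speed.** Assumptions (the documents give no union rates): 75 per arm, no loss, arms truly equal, one-sided 2.5%, 80% power, union seen only at the four radiograph visits. The ratio is immediate over protected, so values below 1 mean slower healing with immediate weight bearing.

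In a complementary log-log model with visit terms, let n be the number per arm not yet united before a visit and h the probability of union at that visit. Then:

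- weight per visit w = n × [ln(1 − h)]² × (1 − h)/h
- SE of the log ratio = 1/√(Σw/2)
- lowest ratio that can be excluded = exp(−2.802 × SE)
- chance of a non-significant difference test at a true ratio of 0.8 = Φ(1.960 − 0.223/SE) − Φ(−1.960 − 0.223/SE), since ln 0.8 = −0.223

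Example, 5/30/60/80% united at 6 weeks and 3, 6 and 12 months: n = 75, 71.25, 52.5, 30; h = 0.05, 0.263, 0.429, 0.50; w = 3.75, 18.60, 21.92, 14.41. Σw/2 = 29.34, SE = 0.185, limit = 0.596.

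| Assumed % united at the four visits | SE | Lowest ratio excluded | Non-significant at true ratio 0.8 |
|---|---|---|---|
| 5/30/60/80 | 0.185 | 0.596 | 77% |
| 10/40/70/85 | 0.179 | 0.605 | 76% |
| 20/60/85/95 | 0.172 | 0.618 | 74% |
| 2/70/78/80 (different shape) | 0.192 | 0.584 | 79% |

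The last column uses the equal-arms SE. Allowing for the slower arm gives 78.2%, 77.0% and 74.9% for the first three rows.

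If 20% were lost and left out (60 per arm), the limits for the first three rows become 0.561, 0.570 and 0.584.

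If the outcome were instead the proportion p united, the deficit that could be excluded is 2.802 × √(2p(1 − p)/75): 18, 16, 14 and 10 points at p = 80, 85, 90 and 95% (approximate at 95%).

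**If incomplete follow-up were applied after randomisation.** Assume equal arms and 20% lost in each. In one arm loss is unrelated to union; in the other it is twice as likely among ununited patients. In that second arm the loss rate among united patients is a = 0.20/(p + 2(1 − p)), and the apparent union among completers is p(1 − a)/0.80. At p = 80%, a = 0.1667 and apparent union is 83.3%; at p = 95%, a = 0.1905 and it is 96.1%. This is a false advantage of about 3 points and 1 point respectively.

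**The case against.** This is a short ethics-board form, and a fuller plan might exist elsewhere. But the form asks for the method and receives a complete answer. The one attachment cited in that section is a literature review, offered for rationale and references.

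A reader might infer that the hypothesis contradicts itself. The documents do not support that. The formal hypothesis is worded the same way both times, and healing no slower includes healing faster. Only the aim and the Potential Benefits answer read as superiority. This is an inconsistency of wording, which matters because no margin is given; it is not the main defect.

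A reader might also infer that patients with incomplete follow-up will be dropped after randomisation. The documents do not say so: the procedures apply the exclusions before patients are told of the study. What stands is that this item cannot be judged at that stage, so its use needs to be stated.

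Finally, the documents name no primary outcome, and union by a fixed visit would serve as well as time to union. That choice belongs to the investigators; the need to make one does not go away.

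**Conclusion.** The concern holds. The plan specifies no inference on its randomised comparison, and its power statement is attached to nothing. It would go too far to say that 75 per group is wrong or too small, since the documents give nothing to test it against. It would also go too far to say that the trial cannot answer its question: randomised arms and time to union are already planned, and only the analysis is missing.

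On size, with 75 per arm, no loss and 80% to 95% united by 12 months, the trial could exclude a healing-rate ratio below about 0.6. At a true ratio of 0.8, a difference test would be non-significant about three times in four. Both figures rest on assumed union rates and shift slightly with the shape of the union curve. The conclusion that an inferential plan is missing rests on none of them. It should be corrected before any comparative result is reported.

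**What to change.** 1. Replace the analysis answer in the Design section. Name one primary healing outcome, for example time to radiographic union with a single cortical threshold fixed in advance. Compare the randomised weight-bearing arms with a model suited to the four radiograph visits (a discrete-time complementary log-log model is one choice), adjusted for fracture type. Report the healing-rate ratio with a 95% confidence interval, and state how death and reoperation before union are counted.
2. Because safety is part of the aim, report between-arm differences with 95% confidence intervals for the complications already listed: implant failure or reoperation, non-union, malunion, infection, DVT, PE and death.
3. Word the objective identically in both places in the Design section and under Potential Benefits. If the no-slower form is kept, conclude it only from the confidence limit against a margin fixed before data by arm are examined, never from a non-significant difference. If data by arm have already been seen, say so and report the estimate and interval only. The Protocol Notes show the study at renewal in 2019, so this must be addressed openly.
4. Analyse all randomised patients as assigned, censor those lost at their last radiograph, and report loss by arm. Remove incomplete follow-up from the exclusions, or state that it is not applied after randomisation.
5. Restate the power sentence with its outcome, effect or margin, alpha and assumed loss.

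An analysis in adherent patients is optional, and possible only where adherence to the assigned weight bearing was recorded; it may not be recoverable for patients already treated.

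The cost is an amendment and modest analysis work, with no new visits or films. Two limits must be disclosed: 150 patients support only a wide margin, and censoring assumes that loss is unrelated to healing.

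### The trial asks which arm heals faster, but time to union gets only descriptive statistics: no between-arm estimate, no place for patients who never unite or die first, and an exclusion that cannot be known at entry

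*Combined protocol and SAP*

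**What the plan says.** In the combined protocol and SAP, the lay summary under Design hypothesises that patients who bear weight at once heal no more slowly than those whose weight bearing is protected. The answer on investigational procedures describes the study as "Reviewing who heals faster with better outcomes based on assignment to full or partial weightbearing". Allocation is random within fracture type: "Patients in both groups will then be randomized into two groups".

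The form then asks how the data will be analysed. The complete answer is "Descriptive statistics will be performed on the following variables in both groups", followed by a list that includes "discharge disposition, return to baseline ambulation, time to union, pain" and, as separate items, non-union, reoperation and death.

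Healing is read at fixed dates: "Radiographs will be taken at 6 weeks, 3, 6 and 12 months to determine radiographic healing".

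Under Subjects, the sample-size rationale is "75 in each group provides 80% power to detect a difference between the groups". The patients who will not be included are listed in the same section, and the list contains "metastatic disease, incomplete follow up, those with questionable ability to bear weight".

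**The concern.** A power statement presupposes a comparison, and the analysis answer contains none. Followed as written, the plan yields two columns of summaries and no estimate with uncertainty for the question that the trial was randomised to answer. The choice of comparison stays open until the data have been seen.

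Time to union is also not an ordinary measurement. A patient who never unites, or who dies before union, has no value. Nothing in the documents says how such patients enter the variable. The easy default is to summarise those who united, which selects patients on an outcome that arises after randomisation.

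Finally, follow-up runs to 12 months, so completeness of follow-up cannot be established when a patient enters. If that exclusion is applied after randomisation, it removes randomised patients, and unequal loss can create or hide a difference between the arms.

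**Working it through.** **1. The plan's own figure.** The 75 per group at 80% power cannot be reproduced, because no endpoint, effect size, alpha, sidedness or test is given. Assuming 1:1 allocation and two-sided alpha 0.05, it corresponds to a standardised mean difference of (1.960 + 0.842) × √(2/75) = 0.457. If all 150 patients unite, it corresponds to a healing hazard ratio of exp(2.802/√(150/4)) = 1.58. Many inputs give 75, so the figure is neither confirmed nor refuted. It shows only that a comparison was intended.

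**2. What a summary among united patients can do.** The film times are from the plan, with 6 weeks taken as 1.38 months. All else is assumed: 75 per arm and non-union of 15% (arm A) vs 25% (arm B). In the first two rows the latent healing times are Weibull, shape 2, median 4 months, identical in both arms. In the last three rows hazards are proportional and non-union means not united at 12 months, so the hazard ratio is ln 0.25 / ln 0.15 = 0.73.

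Mean among united = Σ(film time × proportion first seen united at that film) / proportion united. For the first row:
- A: (0.0792 × 1.38 + 0.2437 × 3 + 0.4669 × 6 + 0.0602 × 12) / 0.85 = 5.13 months.
- B: (0.0792 × 1.38 + 0.2437 × 3 + 0.4271 × 6) / 0.75 = 4.54 months.

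| Assumed mechanism | Mean among united, A vs B (months) | SE of difference | Trials in which B looks faster |
|---|---|---|---|
| Slowest healers are exactly those who fail | 5.13 vs 4.54 | 0.39 | 94% |
| Failure unrelated to speed | 6.15 vs 6.15 | 0.62 | 50% |
| Proportional hazards, exponential | 5.97 vs 6.51 | 0.76 | 24% |
| Proportional hazards, Weibull shape 1.5 | 7.67 vs 8.15 | 0.72 | 25% |
| Proportional hazards, Weibull shape 2 | 8.89 vs 9.29 | 0.65 | 27% |

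The shares come from 200,000 simulated trials. A normal approximation agrees: in the first row Φ(0.60/0.39) ≈ 0.94. On the proportion united by 12 months among all randomised, B comes out ahead in about 5% of trials in every row.

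**3. What dropping patients can do.** Assume identical exponential healing in both arms, with 20% not united at 12 months. Then 1 − √0.20 = 55.3% are united by 6 months. Suppose that a fraction d of those patients misses the 12-month film and is dropped. The 6-month proportion then reads 0.553(1 − d) / (1 − 0.553d).
- d = 10% in one arm: 0.4975/0.9447 = 52.7%.
- d = 30% in the other: 0.3870/0.8342 = 46.4%. The expected false gap is 6.3 points.
- d = 20% in both: 49.7% in each arm. There is no gap, but each reads 5.6 points too low.

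The retained numbers are 75 × 0.945 = 70.9 and 75 × 0.834 = 62.6, so the 95% half-width for that difference is 1.96 × √(0.527 × 0.473/70.9 + 0.464 × 0.536/62.6) ≈ 17 points. The false gap is smaller than the sampling error of one trial.

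**4. What the proposed comparison can deliver.** With 80% united in both arms of 75 (assumed), the 95% half-width is 1.96 × √(2 × 0.8 × 0.2/75) = 12.8 points. For a claim of no worse healing at one-sided 0.025, 80% power requires a margin of 2.802 × 0.0653 = 18.3 points. The documents state no margin.

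**The case against.** A comparison by arm is plainly intended, and this is a short ethics form. That is fair: the procedures and power answers both show the intent. But the form asked for the method, and this is the only answer in the documents.

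The plan never names a mean among united patients. This is correct, and a reader should not infer that it does. The 94% is also a limiting case in which failure is fixed by healing rank. With partial dependence (assumed correlations 0.3 to 0.9) the share is about 59% to 84%, and under proportional hazards that mean ranks the arms correctly about three times in four. A median would put the arm with more non-unions ahead in only about 16% of trials even in the limiting case. It does so mainly by being insensitive: the two medians coincide in roughly 54% to 99% of trials, depending on the mechanism. Non-union, reoperation and death are listed separately, so an imbalance could be seen there.

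A reader might infer that the plan removes randomised patients. The text does not go that far. The entry sits in an eligibility list, procedure 2 applies the exclusions before patients hear about the study, and no step of removal is described. What stands is that the criterion cannot be met at entry and that no analysis-population rule prevents its later use.

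A reader might also infer that the analysis is by fracture type, because the group-assignment answer first uses the word groups in that sense. The procedures and consent text tie group assignment to weight bearing, and 75 of 150 fits the randomised arms. This needs a clarifying phrase and no more.

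A proportion at one film might seem to replace speed. With union seen only at four dates, the proportion united by each film is a direct reading of speed, and all four are to be reported. How many bridged cortices count as union ("Two independent surgeons will review radiographs to determine bridging of 3 or 4 cortices"), reader disagreement and reoperation before union are endpoint definitions. They are separate matters and are not part of this point.

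**Conclusion.** The concern holds in this form: the analysis answer specifies no between-arm estimate, interval or test for the healing-speed hypothesis, although the power statement presupposes one. Patients who never unite or who die first have no place in the variable. The follow-up exclusion, if applied after randomisation, drops randomised patients.

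The size depends wholly on assumptions. Under those tried, a mean among united patients favours the arm with more non-unions in anything from 24% to 94% of trials, so the direction of bias cannot be known beforehand or corrected afterwards by assumption. The 6.3-point false gap rests on a selective loss pattern that the plan permits but does not describe, and it lies within the sampling error of a trial this size.

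The documents do not support saying that the trial intends no comparison, that it will report a mean among united patients, or that it will discard lost patients. This should be put right before analysis.

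**What to change.** 1. In the Design answer on analysis method, compare all randomised patients by assigned weight-bearing arm on the cumulative proportion united at the 6-week, 3-, 6- and 12-month films. Give the between-arm difference with a 95% CI at one film named before data are analysed. Keep patients not united at 12 months in the denominator, treat death before union as a competing event, and censor lost patients at their last film; a union already seen still counts. Do not use mean time among united patients as the comparison.
2. Delete the incomplete-follow-up entry from the exclusions under Subjects, and report losses by arm.
3. Before analysis, either state the margin against which the CI will be read for a claim of no slower healing, or limit the conclusion to the estimate and its CI.
4. As a clarification only, say that the groups in the analysis sentence are the randomised arms.

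The cost is wording and a little more analysis work in standard software, with no new visits, films or patients. Two limits should be stated: censoring assumes that loss is unrelated to healing, and precision will be about ±12.8 points if 80% unite in both arms of 75.
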